11.5.4 Dose Delays and Modifications for DS-3201b

During Cycle 1 of Phase I dose-escalation, which includes the initial 7 days of safety run-in from Day -7 to Day 0, dose delays and modifications for DS-3201b will not be used unless a DLT has been declared for purposes of determining the MTD. The outlined dose delays and modifications for both DS-3201b and irinotecan will be used in all patients in Phase I Cycle 1 if DLT has been declared, in all subsequent cycles of Phase I, and in all cycles of Phase II of this study. If toxicities are encountered, dosing adjustments and delays of DS-3201b and/or irinotecan will be made based on determination of the likely causative agent as outlined above in Sections 11.2 and 11.3. Determination of the likely causative agent will be dependent on the treating physician if they feel that the toxicity is at least possibly related to either or both of the study drugs.

Please refer to Table 2 in Section 9.0 for full details regarding the dose levels for DS-3201b. An abbreviated version of Table 2.0 is shown below for reference.

Dose Level	DS-3201b Dose
Level -1	50 mg once daily
Level 1(Starting Dose)	100 mg once daily
Level 2	150 mg once daily
Level 3	200 mg once daily
Level 4	250 mg once daily
Level 5	300 mg once daily

If dose level reduction below Level -1 is needed to manage toxicity due to DS-3201b, then study treatment with both DS-3201b and irinotecan will be permanently discontinued unless discussed with the study PI.

Table 5.0 Dose Delays and Modifications for Hematologic TEAEs

ADVERSE EVENT GRADE	DOSE MODIFICATION INSTRUCTIONS
≥Grade 4 neutropenia (<0.5 x 10 ⁹ /L per NCI CTCAE v5.0) lasting >7 days	
• Interrupt administration of study drug DS-3201b up to 28 days.• Resume the study drug DS-3201b at the dose before interruption if lasting ≤7 days at a reduced dose (by 1 dose level). If lasting >7 days once resolved to ≤Grade 2
OR	

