
Febrile neutropenia \geq Grade 3
 
OR
 
neutropenia requiring supportive G-CSF therapy*
	
(neutrophil count $\geq 1.0 \times 10^9/L$) after discussion with PI and Daiichi.
 
• If a second dose interruption is required for the same event, then the study drug DS-3201b may be reduced 1 additional dose level for subsequent cycles. Further dose reductions must be discussed with the study PI and Daiichi. If patient is already at the lowest dose of study drug DS-3201b, please discuss with the study PI and Daiichi regarding study continuation or discontinuation decision.• If ANC does not recover to $\geq 1.0 \times 10^9/L$ within 28 days after interrupting study drug DS-3201b and reducing the dose, please discuss with the study PI and sponsor regarding study continuation or discontinuation decision.• Use of G-CSF is allowed for recurrent neutropenia as per treating physician discretion (except in DLT evaluation period in Phase I Dose Escalation). For patients at high-risk of neutropenia as per treatment physician's discretion, G-CSF can be used in the DLT evaluation period in Phase II.• For any dose delays greater than 28 days, decision regarding study continuation or discontinuation should be discussed with the study PI and sponsor.

Grade 4 Thrombocytopenia ($<25 \times 10^9/L$)
 
OR
 
\geqGrade 3 Thrombocytopenia ($<50 \times 10^9/L$) associated with \geqGrade 2 bleeding/ requiring transfusion
 
OR
 
Grade 3 thrombocytopenia ($<50 \times 10^9/L$) lasting >7 days
	
• For Grade 4 Thrombocytopenia: Interrupt administration of study drug DS-3201b up to 28 days.• For Grade 4 Thrombocytopenia: Resume the study drug DS-3201b at a reduced dose (by 1 dose level) if thrombocytopenia recovers to \leqGrade 2 (platelet count $\geq 50 \times 10^9/L$)• For Grade 4 Thrombocytopenia: If a second dose interruption is required due to Grade 4 thrombocytopenia, then the study drug DS-3201b may be reduced 1 additional dose level for subsequent cycles. Further dose reductions must be discussed with the study PI and Daiichi. If patient is already at the lowest dose of study drug DS-3201b, please discuss with the study PI and Daiichi regarding study continuation or discontinuation decision.• For \geqGrade 3 Thrombocytopenia ($<50 \times 10^9/L$) associated with \geqGrade 2 bleeding: First occurrence -

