	
Interrupt administration of study drug DS-3201b up to 28 days. Resume the study drug at a reduced dose (by 1 dose level) once resolved to \leqGrade 2 (platelet count $\geq 50 \times 10^9/L$) or return to baseline levels within 28 days after interrupting study drug, whether transfusion is given or not. The study drug DS-3201b may be resumed at the same dose after discussion with the study PI and Daiichi.
 
• For \geqGrade 3 Thrombocytopenia ($< 50 \times 10^9/L$) associated with \geqGrade 2 bleeding: Second occurrence – Discontinue subject from the study• For \geqGrade 3 Thrombocytopenia ($< 50 \times 10^9/L$) lasting > 7 days: First occurrence - Interrupt administration of study drug DS-3201b up to 28 days. Resume the study drug DS-3201b at a reduced dose (by 1 dose level) once resolved to \leqGrade 2 (platelet count $\geq 50 \times 10^9/L$) or return to baseline levels within 28 days after interrupting study drug• For \geqGrade 3 Thrombocytopenia ($< 50 \times 10^9/L$) lasting > 7 days: Second occurrence – Interrupt administration of study drug DS-3201b up to 28 days. Resume the study drug at a reduced dose (by 1 dose level) once resolved to \leqGrade 2 (platelet count $\geq 50 \times 10^9/L$) or return to baseline levels within 28 days after interrupting study drug• For \geqGrade 3 Thrombocytopenia ($< 50 \times 10^9/L$) lasting > 7 days: Third occurrence - Discontinue subject from the study• For any dose delays greater than 28 days, decision regarding study continuation or discontinuation should be discussed with the study PI and sponsor.
\geq Grade 3 anemia (< 8.0 g/dL) requiring transfusion	
• Interrupt administration of study drug DS-3201b up to 28 days.• Resume the study drug DS-3201b at the dose before interruption once resolved to \leqGrade 2 (hemoglobin levels recovered to ≥ 8.0 g/dL) at least 7 days since transfusion, or baseline value within 28 days after interrupting study drug, or reduce 1 dose level with after discussion with study PI and Daiichi.• If a second dose interruption is required for the same event, then decrease study drug DS-3201b dose by 1

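### The neutropenia restart rule in Table 5.0 gives two DS-3201b doses for events of 7 days or less and none for longer events: a drafting error with limited practical effect

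*Combined protocol and SAP*

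**What the plan says.** Section 11.5.4 applies its dose rules in every Phase II cycle. The neutropenia row of Table 5.0 has three triggers: Grade 4 neutropenia lasting more than 7 days, febrile neutropenia of Grade 3 or higher, and neutropenia that needs G-CSF. Only the first carries a duration.

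After an interruption of up to 28 days, the restart bullet has two sentences. The first is "Resume the study drug DS-3201b at the dose before interruption if lasting ≤7 days at a reduced dose (by 1 dose level", then a closing bracket and a full stop. The second opens "If lasting >7 days once resolved to ≤Grade 2", gives a neutrophil threshold of 1.0 x 10^9/L, and ends "after discussion with PI and Daiichi".

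The next bullet covers a repeat event: "If a second dose interruption is required for the same event, then the study drug DS-3201b may be reduced 1 additional dose level". It continues: "If patient is already at the lowest dose of study drug DS-3201b, please discuss with the study PI and Daiichi". A further bullet, on counts that fail to recover within 28 days, refers to the drug having been interrupted and its dose reduced.

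Section 9.1 reports 100 mg daily as the dose found in Phase I. The only level below it in the Section 11.5.4 dose table is 50 mg daily.

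**The concern.** A restart rule should lead two physicians with the same patient to the same dose. This one does not. The only duration attached to either dose in the first sentence is 7 days or less, so that case receives both the unchanged dose and a one-level reduction. The second sentence has no main verb and no dose.

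The rule sits in a safety table used at two centres. If sites resolve the wording differently, patients with the same event would be treated differently. A short febrile episode could be followed by full dose at one site and half dose at the other. It is also unclear whether a short event needs any neutrophil recovery before restart.

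**Working it through.** No figure in the plan is in dispute, so the check is a reading of the text, followed by simple arithmetic on size.

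**1. The bullet split by duration, as printed.**

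| Event lasted | Dose named | Recovery condition | Discussion step |
|---|---|---|---|
| 7 days or less | Pre-interruption dose, and one level lower | None attached | None attached |
| More than 7 days | None | Grade 2 or better, count at least 1.0 x 10^9/L | PI and Daiichi |

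The break in the table row does not explain this. The full stop comes before the break, and the text after it supplies no dose.

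**2. Which events meet which line.** The Grade 4 trigger already requires more than 7 days, so it always falls on the line with no dose. Febrile and G-CSF-requiring neutropenia carry no duration and can fall on either line. Only these two can reach the line with two doses.

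**3. The other first-restart bullets in Table 5.0.**

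| Event | Default restart dose | Recovery condition | Alternative dose |
|---|---|---|---|
| Grade 4 thrombocytopenia | One level lower ("Resume the study drug DS-3201b at a reduced dose (by 1 dose level) if thrombocytopenia recovers to" Grade 2 or better) | Yes | None |
| Grade 3 or higher thrombocytopenia with bleeding | One level lower | Yes | Same dose, after PI/Daiichi discussion |
| Grade 3 or higher thrombocytopenia over 7 days | One level lower ("Resume the study drug DS-3201b at a reduced dose (by 1 dose level) once resolved to" Grade 2 or better) | Yes | None |
| Grade 3 or higher anemia | Same dose ("Resume the study drug DS-3201b at the dose before interruption once resolved to" Grade 2 or better) | Yes | One level lower, after PI/Daiichi discussion |

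All four name one default dose and a recovery condition. Where a second dose is allowed, it is tied to a discussion. Within this table, only the neutropenia bullet names two doses for one condition with no default.

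**4. Whether other text fills the gap.** Section 11.6 and Table 8.0 set irinotecan doses, and Section 11.6 makes those adjustments independent of DS-3201b. Table 5.1 covers interacting drugs. Table 6.0 covers non-hematologic events. None gives the first DS-3201b restart dose after neutropenia.

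**5. Likely intent.** Moving the full stop gives a sensible rule: same dose for 7 days or less, one level lower for more than 7 days. The thrombocytopenia bullet for events over 7 days supports it by pairing that duration with a reduction. Two later bullets in the neutropenia row are less helpful. The repeat-event bullet speaks of one additional level, and the non-recovery bullet assumes the dose was reduced. Both presuppose a first reduction without limiting it to long events, so a site could reasonably reduce after a short one. The intent is probable, not certain.

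**6. Size.**
- Per fully dosed 21-day cycle: 100 mg x 21 = 2,100 mg; 50 mg x 21 = 1,050 mg; ratio 2,100 / 1,050 = 2.
- New Phase II patients (Section 1.0): 16 - 6 = 10 if the trial stops at stage 1; 31 - 6 = 25 at the maximum.
- These are enrolment ceilings. A patient meets the ambiguity only after a febrile or G-CSF-requiring event that lasts 7 days or less and is at least possibly attributed to DS-3201b. The documents give no rate for that.

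**The case against.** The strongest reply is that this is a copy-edit with one sensible reading, and that few physicians would act on the literal text. The long-event fragment already calls for a discussion with the PI and Daiichi, so the missing dose there would be settled case by case. Both candidate doses are protocol-defined levels. Table 6.0 openly allows a choice between the same dose and one level lower for some events not attributed to DS-3201b, so such a choice is not treated as unsafe in itself. Section 11.5.4 also bases adjustments on the likely causative agent. Neutropenia and neutropenic fever are listed irinotecan toxicities with their own reductions in Table 8.0, so events put down to irinotecan alone need not change the DS-3201b dose.

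Most of this stands, and it limits the weight of the point. It does not remove it. The discussion step, as printed, is not attached to short events. The Table 6.0 choices are worded as choices and cover non-attributed events, so they do not settle this bullet. The later bullets in the row do not say whether a short event should bring a reduction.

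**Conclusion.** The bullet is wrong as written: two doses for events of 7 days or less, none for longer events, and no other text that supplies the answer. It is a drafting error in an operative rule, with limited practical effect. The live ambiguity is mainly a short febrile or G-CSF-requiring event at least possibly attributed to DS-3201b, where a patient on 100 mg could restart at 100 mg or 50 mg, a twofold difference. How many patients would be affected cannot be derived.

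Three stronger readings are tempting, and the documents do not support them:
- A reader might infer that all 10 to 25 new Phase II patients are affected. Those are enrolment numbers; the event, its duration and its attribution each narrow the group.
- A reader might infer that sites may choose any dose alone after a long event. The fragment sends that decision to the PI and Daiichi.
- A reader might infer that a restart at 50 mg makes a second event end treatment automatically. At the lowest dose, the row calls for a discussion on whether to continue.

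Nor does the point touch the Simon boundaries, the error rates or the ORR analysis.

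The conclusion assumes that Phase II dosing is 100 mg daily, as Section 9.1 indicates, and that the 7-day limit refers to the neutropenic event, as it does in the row's first trigger.

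**What to change.** Subject to sponsor and PI confirmation of intent, replace the restart bullet with one sentence that puts the recovery condition first:

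> Once neutropenia has resolved to Grade 2 or better (neutrophil count at least 1.0 x 10^9/L), restart DS-3201b at the pre-interruption dose if the event lasted 7 days or less, or, after discussion with the PI and Daiichi, one dose level lower if it lasted more than 7 days.

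With this order the recovery condition covers both durations, as the other first-restart bullets in the table would lead one to expect. The sponsor should confirm that it is meant to apply to short events.

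Optionally, the repeat-event bullet could refer to one level below the current dose, so that it fits patients who restarted without a reduction.

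The cost is one bullet in one table cell at the next amendment, plus one phrase in the same row if the optional change is taken. Sample size, stopping rules and analyses stay as they are.

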There have been no reports of events of thrombocytopenia, leukopenia, or lymphopenia, which are synonymous PTs of platelet count decreased, WBC count decreased, and lymphocyte count decreased, respectively. There have been 2 subjects who have experienced a TEAE associated with study drug discontinuation: one subject with platelet count decreased (Grade 4) and one subject with cardiac failure who had signs of impaired cardiac function prior to starting therapy with DS-3201b. There have been no reports of *Pneumocystis jiroveci* Pneumonia (PJP). Among the 5 subjects who experienced Cytomegalovirus (CMV), 2 subjects had onset of CMV infection after discontinuation of study drug due to other AEs or disease progression, 2 subjects recovered from the event without dose modification, and 1 subject experienced disease progression before the event recovered. Limited literature is available regarding the frequency of CMV infections in ATL populations. In Study DS3201-A-J201, there have been no subjects with a TEAE of QT interval prolongation. Additionally, there have been no events of torsade de pointe, ventricular tachycardia, syncope, or other ventricular arrhythmia reported thus far. Review of ECG data for all DS3201-A-J201 subjects showed no subjects with QTcF >480 ms and no subjects with an increase from baseline >60 ms. There were no events related to increased histamine levels observed in Study DS3201-A-J201.

Ten subjects are continuing with the study drug. A total of 15 subjects discontinued from the study treatment: of those, 13 subjects discontinued due to progressive disease and per investigator report 2 subjects discontinued due to TEAEs of cardiac failure and platelet count decreased.

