- Evidence of prolongation of QT/QTc interval (e.g., repeated episodes of QT corrected for heart rate using Fridericia's method [QTcF] >450 ms for men and >470 ms for females) ECG from 12-lead electrocardiogram for measurement of corrected QT interval according to the Fridericia formula: electrocardiogram must be registered at rest. For any EKG assessment, if the initial EKG shows a prolonged QTc, then two additional EKGs will be obtained, resulting in three specimens taken after a space of 1 minute, and the mean of the 3 EKGs will be used to determine eligibility and for grading of TRAEs.

- Diagnosed or suspected long QT syndrome, or known family history of long QT syndrome
- History of clinically relevant ventricular arrhythmias, such as ventricular tachycardia, ventricular fibrillation, or Torsade de Pointes
- Uncontrolled arrhythmia (subjects with asymptomatic, controllable atrial fibrillation may be enrolled), or asymptomatic persistent ventricular tachycardia
- Subject has clinically relevant bradycardia of <50 bpm unless the subject has a pacemaker
- History of second- or third-degree heart block. Candidates with a history of heart block may be eligible if they currently have pacemakers, and have no history of fainting or clinically relevant arrhythmia with pacemakers, within 6 months prior to Screening
- Myocardial infarction within 6 months prior to Screening
- Angioplasty or stent graft implantation within 6 months prior to Screening
- Uncontrolled angina pectoris within 6 months prior to Screening
- New York Heart Association (NYHA) Class 3 or 4 congestive heart failure
- Coronary/peripheral artery bypass graft within 6 months prior to Screening
- Uncontrolled hypertension (resting systolic blood pressure >180 mmHg or diastolic blood pressure >110 mmHg)
- Complete left or right bundle branch block
- Patients who are currently taking medications that are known to prolong the QT interval and are clearly associated with a known risk of Torsades de Pointes (TdP) even when taken as recommended. Please see Section 11.6 for a full list of excluded medications. Patients who are able to discontinue any prohibited medication prior to the start of study drug at Day -7 will still be considered eligible for the study.
- Have a known hypersensitivity to any of the components of or known hypersensitivity to either the study drug itself or any of the inactive ingredients in the study drug product.
- Known liver cirrhosis.

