QTc Grade 3 (QTc >500 ms on 2 separate ECGs, or >60 ms change from baseline, as the average from triplicate), regardless of causality OR Grade 4 (Torsade de Pointes, polymorphic ventricular tachycardia, or signs/symptoms of serious arrhythmia), regardless of causality	
 For Grade 3 QTc: Interrupt administration of study drug DS-3201b immediately For Grade 3 QTc: Check and address any potentially contributing factors: 
 Check and correct electrolytes (potassium, calcium, and magnesium) For Grade 3 QTc: If possible, stop any concomitant medications that prolong QTc interval For Grade 3 QTc: Once resolved to ≤Grade 1 (QTc ≤ 480 ms, as the average from triplicate) the study drug DS-3201b may be resumed. For Grade 3 QTc: If causality is attributed to the study drug DS-3201b, reduce dose by 1 dose level in subsequent cycles For Grade 3 QTc: If the QTcF increase is assessed to be attributed to a cause other than the study drug DS-3201b, resume the study drug DS-3201b at the dose level before interruption, or at a reduced dose (by 1 dose level) but the subject must be monitored closely for QT prolongation for the first cycle at the increased dose. For Grade 3 QTc: If a second dose interruption is required due to Grade 3 QTc prolongation, discontinue subject from the study For Grade 3 QTc: For any dose delays greater than 28 days, decision regarding study continuation or discontinuation should be discussed with the study PI and Daiichi. For Grade 4 (Torsade de Pointes, polymorphic ventricular tachycardia, or signs/symptoms of serious arrhythmia), regardless of causality: Interrupt the study drug DS-3201b immediately For Grade 4 (Torsade de Pointes, polymorphic ventricular tachycardia, or signs/symptoms of serious arrhythmia), regardless of causality: Determine if there are any attributing factors such as electrolytes (potassium, calcium and magnesium), concomitant medications, or other factors For Grade 4 (Torsade de Pointes, polymorphic ventricular tachycardia, or signs/symptoms of serious arrhythmia): If causality is attributed to the study drug DS-3201b, discontinue subject from study For Grade 4 (Torsade de Pointes, polymorphic ventricular tachycardia, or signs/symptoms of serious arrhythmia): If causality is not attributed to the study drug DS-3201b, study drug administration of DS-3201b can resume at a reduced dose (by 1 dose level) once resolved to ≤Grade 1 (QTc ≤ 480 ms, as the average from triplicate).

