If DS-3201b needs to be held for any TEAEs as above, irinotecan should be held as well. When both study drugs are held for any particular visit due to TEAEs, counting of dose cycles will hold until their TEAEs have resolved or improved enough to meet protocol guidelines to restart treatment with both study drugs. If both drugs are held longer than 1 cycle (21 days), the treating physician must discuss eligibility for the patient to continue treatment on study with the study PI.

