11.6 Dose Delays and Modifications for Irinotecan

During Cycle 1 of Phase I dose-escalation, which includes the initial 7 days of safety run-in from Day -7 to Day 0, dose delays and dose modifications of irinotecan will not be used unless a DLT has been declared for purposes of determining the MTD. The outlined dose delays and modifications for both DS-3201b and irinotecan will be used in all patients in Phase I Cycle 1 if DLT has been declared, in all subsequent cycles of Phase I, and in all cycles of Phase II of this study. If toxicities are encountered, dosing adjustments and delays of DS-3201b and/or irinotecan will be made based on determination of the likely causative agent as outlined above

in Sections 11.2 and 11.3. Determination of the likely causative agent will be dependent on the treating physician if they feel that the toxicity is at least possibly related to either or both of the study drugs.

Usual clinical practice for dose delay and modification of irinotecan will be used, and dose adjustments will occur independent of DS-3201b dosing adjustments.

Patients should return to pre-treatment bowel function without requiring antidiarrhea medications for at least 24 hours before the next chemotherapy administration. A new cycle of therapy should not begin until the granulocyte count has recovered to $\geq 1500/\text{mm}^3$, and the platelet count has recovered to $\geq 100,000/\text{mm}^3$, and treatment-related diarrhea is fully resolved. Treatment should be delayed 1 to 2 weeks to allow for recovery from treatment-related toxicities. If the patient has not recovered after a 2-week delay, consideration should be given to discontinuing therapy.

If both study drugs are held for any particular visit due to TEAEs, then the patient would restart that same visit when their TEAEs have resolved or improved enough to meet protocol guidelines to restart treatment with either one or both study drugs.

If irinotecan needs to be held for any TEAEs as above, patients will have the option to continue DS-3201b as long as the TEAE is not also attributed to DS-3201b. However, counting of dose cycles will hold until their TEAEs have resolved or improved enough to meet protocol guidelines to restart treatment with irinotecan, regardless of whether patient continues DS-3201b. If both drugs are held longer than 1 cycle (21 days), the treating physician must discuss eligibility for the patient to continue treatment on study with the study PI.

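### Table 6.0 labels a >60 ms QTc change from baseline Grade 3, but its only numeric restart condition is QTc ≤480 ms; below a 420 ms baseline one reading can meet both

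*Combined protocol and SAP*

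**What the plan says.** All the operative text is in the QTc row of Table 6.0, Section 11.5.4.

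- **Hold.** The row's Grade 3 definition has two arms: "QTc Grade 3 (QTc >500 ms on 2 separate ECGs, or >60 ms change from baseline, as the average from triplicate". Either one requires immediate interruption of DS-3201b.
- **Restart after Grade 3.** "Once resolved to ≤Grade 1 (QTc ≤ 480 ms, as the average from triplicate) the study drug DS-3201b may be resumed".
- **Restart after Grade 4 (serious arrhythmia) not attributed to DS-3201b.** Dosing "can resume at a reduced dose (by 1 dose level) once resolved to ≤Grade 1 (QTc ≤ 480 ms, as the average from triplicate".
- **Second hold.** "If a second dose interruption is required due to Grade 3 QTc prolongation, discontinue subject from the study".

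The text after the table ties the second drug to the first: "If DS-3201b needs to be held for any TEAEs as above, irinotecan should be held as well". On eligibility, Section 6.3 sets only upper QTcF limits, excluding repeated values ">450 ms for men and >470 ms for females". Nothing else in the protocol adds a change-from-baseline condition for restarting after a QTc hold.

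**The concern.** The hold rule looks at both an absolute value and a change from baseline. The restart number looks only at an absolute value. A patient who starts with a short QTc can rise by more than 60 ms and still sit under 480 ms, so the restart number is met before anything has resolved.

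The neighbouring hematologic rules in Table 5.0 do not behave this way, because their restart numbers clear the trigger. Platelets below 50 × 10⁹/L hold and 50 or above restarts. Hemoglobin below 8.0 g/dL holds and 8.0 or above restarts. Neutrophils below 0.5 × 10⁹/L hold and 1.0 or above restarts.

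At stake is the dosing of individual patients. Two sites could treat the same ECG differently. A site that follows the number literally could restart DS-3201b, and irinotecan with it, while the hold trigger is still present. If the change then persisted and forced another hold, the row calls for discontinuation. Animal data in Section 17.1 show dose-dependent QTc prolongation, so the rule deserves to be unambiguous.

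**Working it through.** The plan states no figure to reproduce; the check is threshold arithmetic.

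**Inputs**

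- Change trigger: more than 60 ms from baseline, taken as an upward change (Table 6.0).
- Restart number: QTc ≤480 ms (Table 6.0).
- Baseline B: up to 450 ms in men and 470 ms in women, with no lower limit (Section 6.3).
- QTc in Table 6.0 is assumed to be the QTcF of Section 6.3.

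**Step 1: when both conditions hold.** The trigger is QTc > B + 60 and the restart number is QTc ≤ 480. Both are met when B + 60 < QTc ≤ 480. That range is non-empty only if B + 60 < 480, that is, B < 420 ms.

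**Step 2: size of the overlap, in whole milliseconds.** The last column is the highest restart value if a limit of 60 ms above baseline is added, min(480, B + 60).

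| Baseline (ms) | QTc meeting both trigger and restart number | Restart ceiling with added limit |
|---|---|---|
| 385 | 446–480 | 445 |
| 395 | 456–480 | 455 |
| 405 | 466–480 | 465 |
| 415 | 476–480 | 475 |
| 419 | 480 only | 479 |
| 420 to 470 | none | 480 (unchanged) |

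Example: B = 405 and QTc = 470 give 470 − 405 = 65 > 60, so Grade 3 by the row's label, while 470 ≤ 480.

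**Step 3: limit on these ranges.** The trigger is read on a triplicate. Sections 6.3 and 8.1 call for the two extra ECGs when the first shows a prolonged QTc, and the only figures offered for prolongation are the 450 and 470 ms examples. If those figures decide when a triplicate is taken, the reachable range starts at 451 ms in men and 471 ms in women. At B = 385 it becomes 451–480 (men) or 471–480 (women). At B = 405 it is 466–480 (men) or 471–480 (women). The overlap narrows but does not vanish, and the 470 ms example then applies to a man but not to a woman.

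**Step 4: frequency.** Section 3.6 reports for DS3201-A-J201 "no subjects with QTcF >480 ms and no subjects with an increase from baseline >60 ms", with 25 patients enrolled. For 0 of 25, the one-sided 95% upper bound is 1 − 0.05^(1/25) = 0.113, or 11.3%. This is indirect evidence: that study gave 200 mg without irinotecan, whereas Section 9.1 sets 100 mg with irinotecan here. The share of patients with a baseline below 420 ms is not given, so the table shows where the conflict exists, not how often it occurs.

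**The case against.** The strongest reply is that the words already protect the patient. Restart needs ≤Grade 1, and a rise of more than 60 ms is Grade 3 by the same row, so a patient at +65 ms has not resolved. Reading the number alone would lift the hold on the ECG that imposed it and empty the instruction to interrupt. Restart after Grade 3 is also permissive. This safe reading stands, and a reader should not infer that the protocol plainly allows restart during a Grade 3 prolongation. But it requires the site to override the only restart number the row gives.

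Three stronger inferences are tempting and not supported.

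- **That the Grade 4 bullet has the same defect.** Its trigger is arrhythmia, not a change from baseline. The conflict arises there only if the patient is also more than 60 ms above baseline.
- **That patients will be lost to discontinuation or go one to two weeks unmonitored.** Section 11.6 says that when both drugs are held, "then the patient would restart that same visit when their TEAEs have resolved or improved enough to meet protocol guidelines". With ECGs on Days 1 and 8 (Table 3.0), the next scheduled one is 8 − 1 = 7 days after a Day 1 restart or 22 − 8 = 14 days after a Day 8 restart, before the ±4-day window. Both this gap and the second hold presuppose the literal reading, and the gap also presupposes no unscheduled ECG. The row itself calls for electrolyte correction, stopping QT-prolonging drugs where possible, dose reduction if DS-3201b is the cause and close monitoring if it is not. Table 6.0 separately allows a hold for any substantial clinical risk.
- **That the added limit proves recovery to Grade 1.** Grading follows CTCAE 5.0 (Section 11.1), whose QTc grades the protocol does not reproduce. The limit removes the overlap with the Grade 3 trigger; it does not show that +60 ms is Grade 1.

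Rarity also counts for the other side: none of 25 patients in J201, and Section 17.1 lists the QTc prolongation seen clinically as Grade 1.

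**Conclusion.** The inconsistency is real and narrow. For baselines below 420 ms, the row's restart number can be met while its own Grade 3 change criterion is still met, and on the same triplicate. At a 405 ms baseline the affected range is 466–480 ms; at 420 ms and above there is none. This rests on reading the change trigger as an increase and on the table's QTc being the QTcF used for eligibility.

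It is a stated rule that contradicts itself, not a missing detail, but a safe reading is available and the event is probably uncommon. The consequence is confined to individual dosing decisions. Sample size, error rates and the objective response rate test are unaffected. It is a cheap improvement worth making, with medium confidence in its practical importance.

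**What to change.** In the Grade 3 restart bullet of Table 6.0, replace the parenthetical with: *QTc ≤480 ms and ≤60 ms above baseline, as the average from triplicate*. Make the same change in the Grade 4 bullet for consistency; there it matters only for a patient who is also more than 60 ms above baseline.

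This reuses the row's own threshold and removes the overlap with the Grade 3 trigger at every baseline.

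The cost is one phrase in two bullets, and possibly a longer hold of DS-3201b, and of irinotecan with it, for a few patients with low baselines.
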